#### **Phase 2 Randomized Stage**

The Phase 2 segment of the study is an open label, randomized, 2-arm design to evaluate the efficacy and safety of oral AG-221 with SC azacitidine versus SC azacitidine alone. Eligible subjects must have newly diagnosed AML with an IDH2 mutation and, who are not candidates to receive intensive IC based on the investigators assessment.

All subjects discontinued from study treatment for any reason other than withdrawal of consent for follow-up will continue to be assessed for AEs, concomitant medications, concomitant procedures, transfusions, [REDACTED] response, hematologic improvement, subsequent AML therapies, and survival.

- All subjects discontinued from study treatment for any reason except withdrawal of consent for follow-up or disease progression will continue to be assessed during the Follow-up period of the study for response until disease progression (Section 6.3).
- All subjects discontinued from study treatment for any reason except withdrawal of consent for follow-up will continue to be assessed for subsequent AML therapies, and survival (Section 6.3).

The trial will continue until enough EFS events to allow full statistical analysis (Section 9).

See [Figure 3](#): Overall Study Design Phase 1b and [Figure 4](#): Overall Study Design Phase 2.

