#### **3.1.2.4. Phase 2 Follow-up Period**

[figure not shown]
All subjects discontinued from study treatment for any reason other than withdrawal of consent for follow-up will continue to be assessed for AEs, concomitant medications, concomitant procedures, transfusions, [REDACTED] response, hematologic improvement, subsequent AML therapies, and survival.

- All subjects discontinued from study treatment for any reason except withdrawal of consent for follow-up or disease progression will continue to be assessed during the Follow-up period of the study for response until disease progression, relapse, or the start of second line therapy (Section 6.3).
- All subjects discontinued from study treatment for any reason except withdrawal of consent for follow-up will continue to be assessed for subsequent AML therapies, and survival (Section 6.3).

[figure not shown]

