ADT = the last adequate assessment date on or prior to start of subsequent anticancer therapy/randomization date	Y	If a subject died, had MR, or had disease progression by investigator review after receiving subsequent anticancer therapy. If there was no post-baseline response assessment on or prior to start of subsequent anticancer therapy, then ADT = the randomization date.

ADT = analysis date; N=no; Y= yes, MR=morphologic relapse.

Note: Event-free response refers to a response that was neither morphologic relapse(MR), progressive disease (PD) nor death.

Sensitivity analyses for EFS will be done with the following censoring rules:

- Subjects with two or more consecutive missing response assessments prior to an event date (death, MR or disease progression) will be considered as events at the event date by ignoring the missing assessments; (EFS1)

- Subjects with subsequent AML therapy prior to an event date will be considered as events at the event date; (EFS2)
- Analysis of EFS with subjects censored at the time of transplantation after study treatments; (EFS3)

Other sensitivity rules may be added when data is available.

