10.2.2. Duration of Response

Duration of response is defined as time from first documented CR/CRi/CRp/PR/MLFS to documented morphologic relapse, PD, or death due to any cause, whichever occurs first. Subjects without morphologic relapse, PD, or death due to any cause will be censored at the date of the last response assessment.

The duration of response will be analyzed using the KM method. The 25th percentile, median and 75th percentile time (including two-sided 95% CI) will be summarized for each treatment arm. Only subjects with documented CR/CRi/CRp/PR/MLFS response as determined by investigator assessment will be included in the analysis.

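### Duration of response counts deaths after new AML therapy but censors living switchers before it, so censoring time depends on outcome and those deaths are handled opposite to primary EFS

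*SAP*

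**What the plan says.** SAP 10.2.2 runs duration of response from first documented response "to documented morphologic relapse, PD, or death due to any cause, whichever occurs first". Everyone else falls under one rule: "Subjects without morphologic relapse, PD, or death due to any cause will be censored at the date of the last response assessment". SAP 10.2.3 (duration of remission) and 10.2.12 (duration of CR/CRh) use the same construction, and protocol 9.6.2 has it for duration of response in Phase 2. None of these sections mentions subsequent therapy or plans a sensitivity analysis. SAP 10.2 provides Kaplan-Meier estimates, with Cox hazard ratios and log-rank tests as appropriate.

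Primary EFS is different. One row of SAP Table 4 reads "If a subject died, had MR, or had disease progression by investigator review after receiving subsequent anticancer therapy". Its analysis date is "ADT = the last adequate assessment date on or prior to start of subsequent anticancer therapy/randomization date", and it is flagged as censored. Another row censors living subjects on the same date. Counting later events is only a sensitivity analysis: "Subjects with subsequent AML therapy prior to an event date will be considered as events at the event date; (EFS2").

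Protocol 3.1.2.4 has response assessed "for response until disease progression, relapse, or the start of second line therapy", while survival and subsequent therapies continue to be collected (every 4 weeks, protocol 6.3). Protocol 3.1.1.8 says the same for Phase 1b. Other text differs. In protocol 3.1, subjects "will continue to be assessed during the Follow-up period of the study for response until disease progression (Section 6.3"), and the Protocol Summary and SAP 4.1 agree with that. The stopping list in protocol 6.3 does not name second-line therapy. Protocol 9.6.1 follows Phase 1b transplant subjects to progression or end of trial.

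**The concern.** Take two responders who start new therapy, or go to transplant, on the same day without documented relapse. One dies a year later and is an event at death. The other lives and, under protocol 3.1.2.4, is censored at the last marrow before the switch. The length of follow-up is thus decided by the outcome, which is the dependence that Kaplan-Meier censoring must not have.

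The two endpoints also disagree about the responder who died: an event for duration of response, censored for primary EFS. Such subjects are foreseen, since protocol 11.1 lists allogeneic transplant as a reason to stop treatment and SAP 8.4.3 tabulates subsequent therapies and transplants. At stake are the reported durations and any between-arm comparison of them if switching differs by arm.

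**Working it through.** **1. Plan figures.** The plan states no figure for duration of response. Its design figure, 75% power for ORR, reproduces (73.9% with pooled variance, 75.9% unpooled) but has no bearing here. The design does give the expected number of responders: 0.50 × 66 = 33 and 0.30 × 33 = 9.9, about 10.

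**2. The rules side by side**, for a responder who starts new therapy without documented relapse:

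| Later status | Duration of response | Primary EFS (Table 4) | EFS2 |
|---|---|---|---|
| Dies | Event at death | Censored at last adequate assessment on or before therapy | Event at death |
| Alive | Censored at last response assessment (before therapy, under protocol 3.1.2.4) | Censored at last adequate assessment on or before therapy | No change stated |

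Only the first row separates duration of response from primary EFS.

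**3. Direction for a fixed event definition.** Let the event be relapse before new therapy, or any death. The estimate is S(t) = product over event times t_j ≤ t of (1 − d_j/n_j). Keeping living switchers at risk leaves every t_j and d_j unchanged. The as-written rule only lowers n_j to n_j − m_j, where m_j is the number of living switchers already removed. Since 1 − d_j/(n_j − m_j) ≤ 1 − d_j/n_j at every step, the as-written curve cannot lie above the other. For illustration, with 5 at risk at a death and one further living switcher already dropped from those 5, the step is 1/4 rather than 1/5. With about 10 responders in the azacitidine arm, such steps are visible.

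**4. Size.** Only the marrow interval comes from the documents (8 weeks in follow-up, protocol 6.3, taken as 2 months). The rest is assumed:
- exponential time to relapse or death with true median 12 months, so 0.5^(24/12) = 25% at 24 months;
- switching unrelated to prognosis, at 0.01, 0.02 or 0.04 per month (about 11% to 39% of responders);
- median survival after switching of 9, 12 or 24 months;
- data cutoff uniform on 12–36 or 24–48 months;
- no marrow after the switch; 200,000 responders per scenario.

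Selected results, as median in months / 24-month rate:

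| Cutoff | Switch rate | Post-switch survival | As written | Table 4 rule | Deaths counted, survivors kept at risk |
|---|---|---|---|---|---|
| 12–36 | 0.04 | 9 | 10.6 / 14% | 11.5 / 23% | 11.3 / 21% |
| 12–36 | 0.02 | 12 | 11.4 / 20% | 11.8 / 24% | 12.0 / 24% |
| 12–36 | 0.01 | 24 | 11.8 / 22% | 11.9 / 24% | 12.4 / 27% |
| 24–48 | 0.04 | 24 | 12.0 / 23% | 11.5 / 24% | 13.8 / 33% |

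Over all 18 scenarios the as-written median ran from about 10.6 to 12.0 months and the 24-month rate from about 14% to 24%. The Table 4 rule gave 11.5 to 11.9 months; it falls slightly short because it censors back to the last marrow. Against the Table 4 rule, the as-written 24-month rate was always lower, but the median ranged from 0.9 months lower (10.6 − 11.5) to 0.5 higher (12.0 − 11.5).

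**5. A different target.** A second simulation took as truth the time to relapse or death regardless of therapy, including relapse after therapy. It assumed:
- relapse median 12, 18 or 24 months, and 5% per year non-relapse death;
- new therapy at 0% to 35% per year;
- post-therapy median survival 9, 24 or 48 months, with median time to relapse after therapy 0.7 times that;
- cutoff 12–36 months.

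The as-written 24-month estimate ranged from 0.105 too low (0.183 against 0.288) to 0.023 too high (0.267 against 0.244).

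**The case against.** **The premise is partly inferred.** SAP 10.2.2 says the last response assessment, not the last one before new therapy; the latter follows from protocol 3.1.2.4. If protocol 3.1, SAP 4.1 or the stopping list in 6.3 governs, marrows continue after the switch and most of the asymmetry disappears. This stands. It does not remove the disagreement with primary EFS over deaths after new therapy, and it makes reconciliation part of the fix.

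**EFS is less different than it looks.** A reader might infer that EFS and duration of response treat all switchers differently. They do not: living switchers are censored alike. EFS2 counts later deaths and states no change for survivors, so the SAP already contains the same hybrid. But it does so only as a sensitivity analysis, whereas for duration of response it is the sole rule.

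**Downward bias is not general.** A reader might infer that duration of response is always understated. The documents name no estimand, and step 5 shows the sign can reverse. In step 4, with later cutoffs and 24-month post-switch survival, the median barely moves. The largest shift there, 12.0 − 10.6 = 1.4 months, is less than one 2-month marrow interval.

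**No alternative is free of bias.** A reader might infer that any symmetric rule recovers the truth. Censoring at new therapy assumes switching is uninformative. The sponsor's amendment rationale for ending response follow-up there treats a new therapy as progression, which suggests otherwise. Keeping survivors at risk treats them as relapse-free without marrows and gave medians of 11.3 to 13.8 months. Both points stand; they call for stating the assumption and showing both analyses.

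**Conclusion.** The concern holds in a limited form. Read with protocol 3.1.2.4, the rule in SAP 10.2.2, 10.2.3 and 10.2.12 makes censoring time depend on later survival, and it handles deaths after new therapy opposite to primary EFS. The downward direction is certain only for the fixed event definition in step 3, relative to keeping living switchers at risk. An unconditional claim of downward bias is not supported.

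The size cannot be derived from the documents, which give neither the share of responders switching without relapse nor their later survival. The step 4 ranges are illustrative and run from a negligible effect to a loss of about 1.4 months in the median and 11 percentage points at 24 months (25% − 14%). Duration of response is secondary, and the primary ORR test is unaffected. The point should be corrected but does not threaten the trial's main conclusion.

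**What to change.** - Apply Table 4's subsequent-therapy rule to SAP 10.2.2, 10.2.3 and 10.2.12: censor at the last adequate assessment on or before new AML therapy, whatever follows. The fallback date should be first response rather than randomization. Say whether transplant counts as subsequent therapy, since SAP 8.4.3 lists it among AML therapies while EFS3 handles it separately.
- Amend protocol 9.6.2 to match.
- Reconcile protocol 3.1.1.8, 3.1.2.4 and 6.3 with the Protocol Summary, protocol 3.1 and 9.6.1, and SAP 4.1 on when response follow-up stops.
- Add an EFS2-type sensitivity analysis that counts later deaths and keeps living switchers at risk to the date last known alive. State that it treats them as relapse-free, and that the main rule assumes switching is uninformative.
- Report by arm how many responders start new therapy without documented relapse.

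Therapy and survival dates are already collected, so the cost is wording and programming, plus a protocol change. The latest amendment's justification reports a finalized primary study report and mature 24-month duration-of-response data already supplied for a DMC meeting. Any change now should therefore be labelled post hoc and shown beside the as-written result.

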10.2.3. Duration of Remission

Duration of remission is defined as time from first documented CR to documented morphologic relapse, PD, or death due to any cause, whichever occurs first. Subjects without morphologic relapse, PD, or death due to any cause will be censored at the date of the last response assessment.

The duration of remission will be analyzed using the KM method. The 25th percentile, median and 75th percentile time (including two-sided 95% CI) will be summarized for each treatment arm. Only subjects with documented CR as determined by investigator assessment will be included in the analysis.

10.2.4. Overall Survival

Overall survival (OS) is defined as time from first date of study drug (Phase 1b) or randomization (Phase 2) to death due to any cause. This time to event endpoint will be analyzed, similarly to the EFS analyses described in 10.2.1. Sensitivity analysis for OS may be explored if needed.

10.2.5. One-Year Survival

One-year survival is defined as the probability of survival at 1 year from randomization.

One-year survival will be evaluated by KM estimate with 95% CI by treatment arm. Difference between treatment arms and corresponding two-sided 95% CI will also be displayed based on log-rank test. The CI for the difference in the 1-year survival probabilities will be derived using Greenwood's variance estimate.

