For **HRQoL** data, analyses will address the mean differences by treatment group on the EORTC QLQ-C30 scale and subscale scores and the treatment group differences in the proportion of subjects who achieve minimal clinically important differences. EQ-5D-5L will be scored according to the instrument guidance and analyzed accordingly.

Overall survival and one year survival rates will be analyzed using Kaplan-Meier method, and the treatment comparison will be conducted using log-rank test.

The other secondary endpoints include complete remission rate, best overall objective response rate, rate of hematologic improvement (HI), the sponsor assessed CR/CRh (based on laboratory dataset) and duration of CR/CRh. These endpoints will be analyzed using the statistical methods mentioned above or other statistical methods as appropriate. As noted, CRh is not available from the investigator assessment. As a result, the analyses on CR/CRh will be based on the sponsor derived assessment.

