4.4. Sample Size Determination

The Phase 1b dose-finding stage will enroll a total of approximately 24 subjects. Additional subjects may be enrolled in a dose level to replace subjects who are not evaluable for the primary endpoint, or for further exploring safety, PK, PK/pharmacodynamics, or preliminary clinical activity.

In Phase 1b AG-120 expansion stage, to ensure acceptable toxicity at the RCD, up to 15 subjects will be accrued into the AG-120 expansion phase. Based on a sample size of 18 AML subjects treated at RCD (i.e., 15 subjects in the dose expansion and around 3 subjects in the dose escalation), there is 95% probability of detecting 1 or more AEs with an underlying rate of 15%, and 85% probability of detecting 1 or more AEs with an underlying rate of 10%.

In Phase 2 AG-221 randomized stage, subjects with AML with IDH2 mutation will be randomized to receive oral AG-221 + SC azacitidine versus SC azacitidine in a 2:1 ratio. A minimum of 99 subjects will be randomized in this phase with 66 subjects in the oral AG-221 + SC azacitidine arm, and 33 subjects in the SC azacitidine monotherapy arm. The statistical comparisons will be conducted for oral AG-221 + SC azacitidine versus azacitidine monotherapy. Assuming an ORR of 30% in the azacitidine monotherapy and an ORR of 50% for oral AG-221 + SC azacitidine arm, the sample size of 66 subjects in AG-221 + SC azacitidine arm and 33 patients in SC azacitidine monotherapy arm will provide 75% power to detect a 20% difference in ORR at a two-sided type I error rate of 0.2. The multiple comparisons were not considered in the sample size calculation.

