10. EFFICACY ANALYSIS

All efficacy analyses will be conducted separately for Phase 1b and Phase 2. All efficacy analysis will be performed on the FAP population (Phase 1b) and on the ITT population and mITT as well (Phase 2) unless otherwise specified. Key efficacy analyses will also be performed on EAP supportive evidence and to assess the robustness of the efficacy findings for both Phase 1b and Phase 2. Subjects will be analyzed according to either dose cohort (Phase 1b) or randomized treatment arm (Phase 2).

All statistical tests will be two-sided at the significance level of $\alpha=0.05$ unless otherwise specified, and the corresponding p-values and two-sided 95% confidence interval (CI) for intended point estimates will be reported, unless specified otherwise.

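### SAP 10.2.5 bases the one-year survival difference and its CI on the log-rank test, which provides neither; the Greenwood interval in the next sentence is sound, but no 12-month test is named

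*SAP*

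**What the plan says.** SAP 10.2.5 defines the endpoint at a single time point: "One-year survival is defined as the probability of survival at 1 year from randomization". Each arm is to be estimated in the matching way: "One-year survival will be evaluated by KM estimate with 95% CI by treatment arm". Two sentences on the between-arm comparison follow. The first reads "Difference between treatment arms and corresponding two-sided 95% CI will also be displayed based on log-rank test". The second reads "The CI for the difference in the 1-year survival probabilities will be derived using Greenwood's variance estimate".

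Protocol 9.6.2 covers overall survival (OS) and one-year survival together: "Overall survival and one year survival rates will be analyzed using Kaplan-Meier method, and the treatment comparison will be conducted using log-rank test". Neither document names any other test for the one-year comparison or limits the log-rank test to the first 12 months.

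The endpoint tables in both documents list one-year survival as a Phase 2 secondary endpoint separate from OS. SAP 10.2.4 analyses OS in the same way as EFS, which uses the log-rank test and a Cox model. SAP 10 sets the general rule for efficacy tests ("All statistical tests will be two-sided at the significance level of" 0.05 unless otherwise specified), with p-values and 95% intervals reported.

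**The concern.** The log-rank statistic sums observed minus expected deaths over all event times. It tests whether the two curves are equal throughout follow-up. It contains no estimate of the difference in survival at month 12, and no interval for that difference can be obtained from it. The first SAP sentence therefore cannot be carried out as written, and it gives the same interval a different basis from the second.

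What is at stake is a table that contradicts itself. If the named test is used, the 12-month difference and its Greenwood interval would sit beside a p-value that answers another question. SAP 4.1 expects about 30 months per subject in Phase 2, so deaths well after month 12 would enter that p-value. It would also be the OS p-value over again, shown under a second endpoint as though it were separate evidence.

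**Working it through.** **1. The plan's own figure.** SAP 4.4 gives one Phase 2 power figure: "will provide 75% power to detect a 20% difference in ORR at a two-sided type I error rate of 0.2", for 66 vs 33 subjects and ORR 50% vs 30%.
- Pooled rate: (33×0.30 + 66×0.50)/99 = 0.433.
- Null SE: √[0.433×0.567×(1/33+1/66)] = 0.1057. Alternative SE: √(0.21/33 + 0.25/66) = 0.1008.
- Power: Φ[(0.20 − 1.2816×0.1057)/0.1008] = 73.9%. With unpooled variance it is 75.9%, and by exact enumeration of the chi-square test 75.3%.

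The stated 75% reproduces. It concerns ORR only. No survival rate, event count or power is stated for one-year survival.

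**2. Inputs for the illustration.**
- From the SAP: 66 vs 33 subjects (4.4), two-sided 0.05 (10), Kaplan-Meier with Greenwood variance at 12 months (10.2.5).
- Assumed, because the documents are silent: the hazards below, and administrative censoring uniform from month 12 to month 30 or 36.

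Two tests are compared on the same simulated trials: the log-rank test over all follow-up, and z = (S₁ − S₀)/√(V₁ + V₀) at 12 months with Greenwood variances.

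**3. Proportional hazards, control median 12 months, hazard ratio 0.6, censoring to month 30 (5,000 trials).** One-year survival is 0.50 vs 0.50^0.6 = 0.660, a difference of 0.160.
- Hand check of the 12-month test: nobody is censored before month 12, so Greenwood reduces to S(1−S)/n. SE = √(0.25/33 + 0.660×0.340/66) = 0.105, z = 1.52, power about 33%. Simulated: 34.2%.
- Hand check of the log-rank test: about 56 deaths, V = 56×(2/3)×(1/3) = 12.4, z = 0.511×√12.4 = 1.80, power about 44%. Simulated: 47.1%.
- The verdicts differ in 21.7% of trials: log-rank alone significant in 17.3%, the 12-month test alone in 4.4%.

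With no difference at all, the two tests reject in 5.5% and 5.8%, and their verdicts differ in 5.5%.

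**4. Equal 60% one-year survival, separation only afterwards.** The hazard to month 12 is −ln(0.6)/12 = 0.0426 per month in both arms.

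| Hazards after month 12 | Log-rank rejects | 12-month test rejects |
|---|---|---|
| Late hazard ratio 0.5 | about 9-11% | 5-6% |
| Fourfold difference, range over patterns and follow-up | about 15-67% | 5-6% |

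The fourfold range is wide because the ratio alone does not fix the answer. With censoring to month 36, the log-rank rejection rate was about 22% when only the combination hazard fell (to a quarter), 42% when the control hazard doubled and the combination hazard halved, and 62% when only the control hazard rose (fourfold). No single figure from this range should be quoted as the size of the problem.

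**5. The reverse case (control median 12 months, censoring to month 30).** With hazard ratio 0.4 to month 12 and 2.0 afterwards, the one-year difference is 0.50^0.4 − 0.50 = 0.258. The 12-month test rejects in 72.1% of trials and the log-rank test in 15.6%; the verdicts differ in 57.7%.

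**The case against.** The strongest reply is that the same paragraph largely repairs the fault. The endpoint, the estimate in each arm and the interval for the difference are all specified correctly once the Greenwood sentence is read, and that 95% interval already gives a fixed-time verdict at 0.05. This stands. A reader might infer that no valid interval is planned for the one-year difference; the Greenwood sentence rules that out.

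A reader might also infer that the SAP commits to printing a log-rank p-value as the one-year p-value. It does not say so. Section 10.2.5 names no p-value, and the SAP 10.2 list of time-to-event variables whose p-value comes from the log-rank test omits one-year survival. Protocol 9.6.2 can be read as one comparison of the curves with one-year rates as read-outs, and Protocol 9 leaves final methods to the SAP. These points narrow the concern without removing it. The protocol sentence still names the log-rank test as the comparison for one-year survival, and the SAP repeats the link instead of replacing it with a 12-month test.

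Finally, a log-rank rejection when one-year survival is equal is not a false positive: in those simulations the curves do differ, and the rejection is correct for OS. It misleads only if presented as a one-year result.

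**Conclusion.** The wording is wrong and the two adjacent SAP sentences conflict. The valid interval is recoverable; what is missing is a test that matches the endpoint. The only test named repeats the OS comparison and can disagree with the 12-month interval at this trial's size: in about 22% of trials under proportional hazards with hazard ratio 0.6, and more or less often under other patterns. All of these rates rest on assumed hazards and censoring that the documents do not give, so they show that disagreement is possible and roughly how large it could be; they do not predict it.

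The consequence is small. One-year survival is one of many Phase 2 secondary endpoints, and no testing hierarchy or alpha allocation was found to rest on it. A reader might infer that the efficacy conclusion is at risk, but the primary ORR test does not use this endpoint.

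**What to change.** In SAP 10.2.5, delete the words that base the difference and its interval on the log-rank test. State that the between-arm difference, its two-sided 95% CI and any p-value come from the 12-month Kaplan-Meier estimates with the Greenwood variance already specified, on the same scale so that the interval and p-value agree. Keep the log-rank test for OS in SAP 10.2.4. Align Protocol 9.6.2 by separating one-year survival from the OS comparison, or record the departure from the protocol in the SAP.

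The cost is one SAP sentence plus the protocol alignment or note. No change to data collection, sample size or the primary analysis is needed.
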